2.1 Study rationale and purpose

Ruxolitinib, a potent and selective inhibitor of JAK1 and JAK2 is indicated for treatment of disease-related splenomegaly or symptoms in adult patients with myelofibrosis (MF). Ruxolitinib effectively treats MF symptoms, spleen enlargement, and provides an overall survival benefit compared to placebo or best supportive care. Thrombocytopenia has been observed in patients with MF treated with ruxolitinib and is one of the key dose-limiting toxicity. Transient hemoglobin drops have also been observed in MF patients treated with ruxolitinib and typically reach a nadir between weeks 8 and 12, returning to levels close to baseline towards week 24.

While anemia was adequately managed for patients to continue in the phase III trials by dose adjustments and supportive interventions instituted at Investigator's discretion, the phase III study protocols did not define any specific dose modifications for patients with new onset or continuing anemia. Many events of Grade 3/4 anemia were treated with transfusions, therefore the proportion of patients receiving transfusions on study peaked around Week 12 of

treatment and then declined to levels similar to the control groups, mirroring the profile for Grade 3/4 anemia incidence ([Verstovsek 2012](#)).

Anemia is one of the diagnostic criteria for myelofibrosis and a known adverse prognostic factor. In the International and Dynamic International Prognostic Scoring Systems, Hb levels of <100 g/L at the time of diagnosis and during the course of disease, respectively, have been shown to have a significant negative impact on overall survival (OS). However, both scoring systems were derived and validated prior to the availability of ruxolitinib; additional analyses from COMFORT studies characterized the effect of ruxolitinib treatment on the Hb dynamics and did assess its impact on OS ([Al Ali 2016](#)); consistent with validated prognostic models, baseline anemia was associated with decreased OS in the COMFORT studies. Treatment with ruxolitinib improved OS as compared with the control arm regardless of baseline anemia status. Notably, post baseline anemia that occurred on ruxolitinib therapy did not impact OS and was manageable with dose adjustments and RBC transfusions concluding that early onset ruxolitinib-related anemia does not have the same deleterious effect as disease-related anemia. ([Gupta 2015](#))

Considering the typical hemoglobin level for many MF patients is already at the Grade 0/Grade 1 border (hemoglobin of 10 g/dL), assessment of a dose regimen that might provide clinically meaningful symptomatic and spleen size reduction benefits of ruxolitinib while lessening the degree of worsening hemoglobin levels is warranted.

Current label recommendation on starting doses in MF are 5, 15 or 20 mg BID, depending on platelet counts $50-100 \times 10^9/L$, $100-200 \times 10^9/L$ or $>200 \times 10^9/L$ respectively, regardless of hemoglobin level at baseline.

There is increasing literature suggesting the use of lower starting doses with up titrations depending on safety and efficacy in patients with anemia ([Tabarroki 2013](#), [Cervantes 2014](#), [Reilly 2014](#), [Harrison 2013](#), [Ho 2015](#)).

This multicenter phase II open label single arm study proposes to prospectively evaluate a starting dose of ruxolitinib 10 mg BID for 12 weeks with subsequent up titrations of 15mg BID and 20 mg BID in anemic myelofibrosis patients defined as a baseline hemoglobin < 10 g/dL (Please see [Figure 6-1](#) for details). The trial will evaluate if this alternative dosing approach achieves spleen reduction and symptom improvement to levels consistent with those reported in previous clinical trials but with an improved tolerability assessed by incidence of adverse events and transfusion requirements.

[figure not shown]
[figure not shown]
2.2 Rationale for the study design

The COMFORT studies compared the effects of ruxolitinib with placebo or best available therapy, respectively and showed that ruxolitinib treatment significantly reduced splenomegaly and provided marked improvements in MF-related symptoms and quality-of-life (QOL) measures compared with controls, regardless of JAK2V617F mutational status. The clinical benefit and safety of ruxolitinib treatment in COMFORT -I and COMFORT-II have been maintained with subsequent longer-term follow-up. As anticipated, the effect of JAK2 inhibition on hematopoiesis resulted in dose-dependent anemia and thrombocytopenia. The majority of these cytopenias occurred in the first 8 to 12 weeks of treatment, and they were generally manageable with dose reductions and/or red blood cell transfusions.

There is increasing literature suggesting the use of a 10 mg BID starting dose with subsequent up titrations depending on safety and efficacy in patients with anemia at the time of treatment initiation with ruxolitinib (Tabarrokhi 2013, Cervantes 2014, Reilly 2014, Harrison 2013, Ho 2015). This dosing approach for anemic MF patients will be systematically studied in this prospective multicenter phase II open label single arm trial to determine if the levels of spleen length reduction and symptom improvement are consistent with those reported in previous clinical trials with ruxolitinib in patients with anemia and doses according to platelet counts at the moment of treatment initiation, and whether this lower starting dose and up titration approach may minimize the initial hemoglobin and platelet declines and transfusion requirements. The efficacy and safety of ruxolitinib with starting doses based on platelet counts in MF patients including those with anemia at baseline have been well studied and characterized in several clinical trials (COMFORT I, COMFORT II, JUMP).

This is an open-label, single-arm study of treatment with ruxolitinib for 48 weeks in patients who presents with transfusion dependent or independent anemia at screening defined as an hemoglobin <10 g/dL.

Ruxolitinib will be self-administered as BID oral treatment. The starting dose is 10 mg BID for all enrolled patients and gradual up titrations will start at week 12 determined by the level of efficacy achieved and the tolerability.

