2.6 Risks and benefits

The primary clinical risks with ruxolitinib treatment are the potential consequences of decreased hematopoietic proliferation secondary to the inhibition of growth factor pathways associated with JAK2 inhibition. Dose-dependent, reversible thrombocytopenia has been observed in patients with MF and represents the DLT. Anemia and, less frequently, neutropenia have also been observed in patients with MF treated with ruxolitinib. Increased rates of infection and anemia are potential risks of myelosuppression, and there are other consequences of anemia including the burden and risks of transfusion.

Of note, the dosing approach proposed in this study may decrease the risk of patients developing cytopenias compared to the standard dose approach utilized in the two phase III pivotal studies.

A dose escalation starting at week 12 aims to achieve a maintenance dose for each patient that maximizes the benefits from ruxolitinib while keeping the treatment well tolerated. The main potential benefit of the proposed dosing approach in the study resides in achieving similar levels of efficacy seen in previous clinical trial experiences with an improved safety and tolerability profile expressed by lower rates of cytopenias and transfusion requirements.

Appropriate eligibility criteria, as well as specific dose modification and stopping rules, are included in this protocol. The risk to patients in this trial may be minimized by compliance with the eligibility criteria and study procedures, as well as and close clinical monitoring. There may be unforeseen risks with ruxolitinib which could be serious. Please refer to the latest [Investigator Brochure].

3 Objectives and endpoints

Objectives and related endpoints are described in [Table 3-1](#) below.

[figure not shown]
[figure not shown]
[figure not shown]

Table 3-1 Objectives and related endpoints

Objective	Endpoint	Analysis
Primary		
To determine the spleen length response rate at week 24.	Proportion of patients achieving a 50% reduction in spleen length at week 24.	Refer to Section 10.4
Secondary		
To evaluate safety.	Safety will be assessed by 
 • Frequency and severity of adverse events and serious adverse events and AEs leading to discontinuations. • Changes in hematology/biochemistry parameters over time. 	Refer to Section 10.5.1

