5.3 Exclusion criteria

Patients eligible for this study must not meet **any** of the following criteria:

1. Patients with prior treatment with any JAK1 or JAK2 inhibitor.
2. Patients with known hypersensitivity to ruxolitinib or other JAK1/JAK2 inhibitors, or to their excipients.
3. Patients eligible for hematopoietic stem cell transplantation (suitable candidate and a suitable donor is available).
4. Patients with inadequate bone marrow reserve at baseline as demonstrated by at least one of the following:
 - a. ANC that is $\leq 1,000/\mu\text{L}$.
 - b. Platelet count that is $< 50,000/\mu\text{L}$ without the assistance of growth factors, thrombopoietic factors or platelet transfusions.
 - c. Hemoglobin count that is ≤ 6.5 g/dL despite transfusions.
5. Patients with severely impaired renal function defined by:
Creatinine clearance less than 30 mL/min.
6. Patients with inadequate liver function defined by any of these:
 - a. Total bilirubin ≥ 2.5 x ULN and subsequent determination of direct bilirubin ≥ 2.5 x ULN;
 - b. Alanine aminotransferase (ALT) > 2.5 x ULN;
 - c. Aspartate aminotransferase (AST) > 2.5 x ULN.
7. Patients being treated concurrently with a strong (potent) systemic inhibitor or inducer of CYP3A4 at the time of Screening.
8. Presence of active bacterial, fungal, parasitic, or viral infection which requires therapy.
9. Known history of human immunodeficiency virus (HIV) infection or other immunodeficiency syndromes such as X-linked agammaglobulinemia and common variable immune deficiency.

10. Acute viral hepatitis or active chronic hepatitis B or C infection. Patients with *inactive* chronic infection (without viral replication) can be enrolled (See [Section 7.2.2.7](#))
11. History of progressive multifocal leuko-encephalopathy (PML).
12. Impairment of gastrointestinal (GI) function or GI disease that may significantly alter the absorption of ruxolitinib (e.g., ulcerative diseases, uncontrolled nausea, vomiting, diarrhea, malabsorption syndrome, small bowel resection).
13. History or current diagnosis of uncontrolled or significant cardiac disease, including any of the following:
 - a. Myocardial infarction within last 6 months
 - b. Uncontrolled congestive heart failure
 - c. Unstable angina within last 6 months
 - d. Clinically significant (symptomatic) cardiac arrhythmias (e.g. bradyarrhythmias, sustained ventricular tachycardia, and clinically significant second or third degree AV block without a pacemaker)

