6.2.3 Guidelines for dose escalations

Dose up titrations will be based on efficacy and platelet counts provided that ANC is $>500 \mu\text{L}$ and Hb level is $\geq 6.5 \text{ g/dL}$ as follows:

- A dose of 15 mg BID should be targeted in patients with platelet count $\geq 100 \times 10^9/\text{L}$ and $\leq 200 \times 10^9/\text{L}$ from week 12. This dose increase is optional for patients that achieved a $\geq 50\%$ reduction in spleen length at this visit relative to Baseline.
- A dose of 20 mg BID should be targeted in patients with platelet count $\geq 200 \times 10^9/\text{L}$ from week 16. This dose increase is optional for patients that achieved a $\geq 50\%$ reduction in spleen length at this visit relative to Baseline.
- Maximum dose allowed in the study is 25 mg BID and may be used from Week 20 in patients that did not achieve a 50% reduction in spleen length relative to Baseline and provided that platelet count is $\geq 200 \times 10^9/\text{L}$ at this visit.
- Patients who did not qualify for a dose increase at Week 12, may qualify for an increase at week 16 (from 10 mg BID to 15 mg BID). In that case, the Week 12 dose increase rules will apply. Similarly, patients who did not qualify for a dose increase at Week 16, may qualify for an increase later (from 15 mg BID to 20 mg BID). In that case, the Week 16 dose increase rules will apply.

Figure 6-1 Dosing Up-titration Diagram

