4.2 Posology and method of administration

Jakavi treatment should only be initiated by a physician experienced in the administration of anti-cancer agents.

A complete blood cell count, including a white blood cell count differential, must be performed before initiating therapy with Jakavi.

Complete blood count, including a white blood cell count differential, should be monitored every 2-4 weeks until Jakavi doses are stabilised, and then as clinically indicated (see section 4.4).

Posology

Starting dose

The recommended starting dose of Jakavi in myelofibrosis is 15 mg twice daily for patients with a platelet count between 100,000/mm³ and 200,000/mm³ and 20 mg twice daily for patients with a platelet count of >200,000/mm³. The recommended starting dose of Jakavi in polycythaemia vera is 10 mg given orally twice daily.

There is limited information to recommend a starting dose for patients with platelet counts between 50,000/mm³ and <100,000/mm³. The maximum recommended starting dose in these patients is 5 mg twice daily and the patients should be titrated cautiously.

Dose modifications

Doses may be titrated based on safety and efficacy. Treatment should be discontinued for platelet counts less than 50,000/mm³ or absolute neutrophil counts less than 500/mm³. In PV, treatment should also be interrupted when haemoglobin is below 8 g/dl. After recovery of blood counts above these levels, dosing may be re-started at 5 mg twice daily and gradually increased based on careful monitoring of complete blood cell count, including a white blood cell count differential.

Dose reductions should be considered if the platelet count decreases below 100,000/mm³, with the goal of avoiding dose interruptions for thrombocytopenia. In PV, dose reductions should also be considered if haemoglobin decreases below 12 g/dl and is recommended if it decreases below 10 g/dl.

If efficacy is considered insufficient and blood counts are adequate, doses may be increased by a maximum of 5 mg twice daily, up to the maximum dose of 25 mg twice daily.

The starting dose should not be increased within the first four weeks of treatment and thereafter no more frequently than at 2-week intervals.

The maximum dose of Jakavi is 25 mg twice daily.

Dose adjustment with concomitant strong CYP3A4 inhibitors or fluconazole

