2.2.4 Subgroup of interest

Not Applicable.

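### For eligible patients with platelets of 50-<100 x10^9/L, 10 mg BID is a higher start than platelet-based dosing, not a lower one, and no readable analysis separates them from the rest.

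*Protocol*

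**What the plan says.** - **Question.** The Protocol summary and Protocol 2.2 ask "whether this lower starting dose and up titration approach may minimize the initial hemoglobin and platelet declines and transfusion requirements". The reference is earlier ruxolitinib trials dosed by platelet count; Protocol 2.2 names COMFORT I, COMFORT II and JUMP. Protocol 2.6 adds that "the dosing approach proposed in this study may decrease the risk of patients developing cytopenias compared to the standard dose approach" of the two pivotal studies.
- **Entry.** The platelet criterion in exclusion 4b (Protocol 5.3) is a count below 50 x10^9/L "without the assistance of growth factors, thrombopoietic factors or platelet transfusions". Counts of 50-<100 are therefore eligible.
- **Starting dose.** 10 mg BID for all enrolled patients (Protocol 2.2, 6.1.1).
- **Platelet-based dosing.** Protocol 2.1: "Current label recommendation on starting doses in MF are 5, 15 or 20 mg BID, depending on platelet counts" of 50-100, 100-200 and above 200 x10^9/L. The label in Appendix 6 (its section 4.2) says of 50-<100: "The maximum recommended starting dose in these patients is 5 mg twice daily and the patients should be titrated cautiously".
- **Rationale for the low range.** Protocol 2.3 and 6.2.1 cite a phase Ib study (EXPAND) reporting a maximum safe start of 10 mg BID at 50-75 and 15 mg BID at 75-100. The same sections say that study 258 and JUMP started patients at 50-100 on 5 mg BID.
- **Titration.** Protocol 6.2.3: "A dose of 15 mg BID should be targeted in patients with platelet count" of 100-200 x10^9/L, from Week 12. A patient who does not qualify then may qualify at Week 16.
- **Analysis.** The FAS and Safety set contain all treated patients (SAP 2.2.1, 2.2.2). No per-protocol exclusion concerns platelets (SAP 2.2.3). SAP 2.2.4, on subgroups of interest, reads "Not Applicable".

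**The concern.** The question depends on the study start being lower than the platelet-based start used before. That is true at platelets of 100 and above. At 50-<100 the direction reverses, and the other half of the regimen, the increase, is not open until the count reaches 100.

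Baseline platelets also predict the safety outcome. The Protocol's account of the phase I/II study and label section 4.4 both report more thrombocytopenia when the starting count is below 200. A pooled cytopenia, platelet-change or transfusion result therefore mixes patients started below label dosing with higher-risk patients started above it. If the pooled result looks no better than the earlier trials, a reader cannot tell whether the lower start failed or whether some patients never had one. If it looks better, the reader cannot tell whether that extends to 50-<100.

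**Working it through.** **1. Starting dose relative to the label** (10 mg BID divided by the label start in Protocol 2.1 and Appendix 6)

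| Baseline platelets (x10^9/L) | Label start (mg BID) | Ratio |
|---|---|---|
| 50-<100 | 5 | 10/5 = 200% |
| 100-200 | 15 | 10/15 = 67% |
| >200 | 20 | 10/20 = 50% |

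**2. What the reference trials offer at 50-<100.** The COMFORT starting doses cover platelets from 100 upward (Protocol 2.3). The label's section 4.8 puts all 301 ruxolitinib patients in the two pivotal studies at 100-200 (111) or above 200 (190). The statement in Protocol 2.6 therefore has no pivotal comparator in this range. JUMP does include 50-100, but at 5 mg BID, so a comparison with it is against a lower start.

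**3. Titration.** The threshold of 100 in Protocol 6.2.3 applies to the on-study count from Week 12, not to the baseline count. The increase is closed while the count stays below 100 and opens if it rises. Separately, Table 6-3 gives a maximum of 15 mg BID at 75-<125 after an interruption or reduction, whereas 6.2.3 sets 100 as the floor for 15 mg BID.

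**4. The plan's design figures.** With the Beta(1/3, 1) prior and 13/50 responders, the posterior is Beta(13.33, 38), and P(rate <= 15%) = 0.0243, as stated. For X ~ Bin(50, p), P(X >= 13) = 0.0301 at p = 0.15 and 0.9339 at p = 0.35, as stated. These figures assume one common response rate and are correct on that basis.

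**5. Effect of a different rate in the low-platelet group.** The documents give neither the share nor the response rate of this group, so both are assumed. Let s patients respond at rate r and the other 50 - s at 35%. The pooled true rate is [s*r + (50 - s)*0.35]/50, and the chance of success is P(Bin(s, r) + Bin(50 - s, 0.35) >= 13), from the exact convolution.

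| s | r = 10% | r = 20% | r = 35% | r = 40% |
|---|---|---|---|---|
| 5 | 0.876 | 0.902 | 0.934 | 0.943 |
| 10 | 0.783 | 0.858 | 0.934 | 0.951 |
| 15 | 0.652 | 0.802 | 0.934 | 0.958 |

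For s = 10 and r = 10% the pooled rate is (10*0.10 + 40*0.35)/50 = 30%; for r = 40% it is (10*0.40 + 40*0.35)/50 = 36%.

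**6. Precision of a separate report.** Exact (Clopper-Pearson) 95% intervals are 1-72% for 1/5, 3-56% for 2/10 and 4-48% for 3/15.

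**The case against.** The best defence is that the dose in this range is disclosed and reasoned. Protocol 2.3 and 6.2.1 cite phase Ib data in which 10 mg BID is at or below the reported maximum safe start across 50-100, and Table 6-2 leaves 10 mg BID unchanged until platelets fall below 50. A trial dose that departs from the label for a stated reason is not an error in itself. This stands. It supports tolerability, however; it does not make 10 mg BID a lower start than the label or JUMP.

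The primary objective is the Week 24 response under this regimen, judged against fixed thresholds of 15% and 25%. No readable analysis formally tests against label dosing. This also stands: a reader might infer that low-platelet patients invalidate the primary result, and they do not.

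Two other strong readings fail. One is that these patients can never be increased; the rule uses the on-study count and allows later qualification. The other is that they lower the power. Nothing in the documents shows a lower response rate in this range. The phase Ib report of spleen length reductions in 17 of 20 patients with platelets of 50-99 is not the 50% Week 24 endpoint, but it does not point to 10-20% either.

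Finally, subgroup estimates at this size will be imprecise, and some analysis sections are blacked out, so the absence of a platelet breakdown can be asserted only for the readable text. Both points stand.

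**Conclusion.** The concern holds for the lower-start question. For an eligible group the study start is twice the label's maximum start and twice the JUMP start, and the first increase is closed while the count stays below 100. The readable analyses do not separate this group, so the pooled hemoglobin, platelet, cytopenia and transfusion results cannot cleanly show what a lower start does.

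The dose ratios come directly from the documents. The size of the mixing does not, because the share of such patients is not given. The change in success probability could go either way and should not be read as a demonstrated loss. The stated operating characteristics are correct, and the FAS primary analysis needs no change.

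**What to change.** 1. **SAP 2.2.4.** Replace the present entry with descriptive baseline platelet groups of 50-<100, 100-200 and >200 x10^9/L, plus >=100 combined. For each, report Week 24 response, grade 3/4 cytopenias, hemoglobin and platelet change to Week 12, transfusions and dose reached. Keep the primary analysis on the FAS.
2. **Protocol summary, 2.2 and 2.6.** Limit the conclusion about a lower start and lower cytopenia risk to platelets >=100. For 50-<100, state that the comparison with JUMP is against a lower start.
3. **Reconciliation by the sponsor.** Protocol 2.1, the appended label (section 4.2) and Protocol 2.3 need to be reconciled with the single starting dose for 50-<100, and Protocol 6.2.3 with Table 6-3. This review proposes no dose.

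The cost is wording and a few tables from data already collected. The low-platelet estimates will be imprecise (2/10 gives 3-56%) and should be presented as descriptive only.

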2.3 Rationale for dose and regimen selection

Phase I/II trials evaluated a number of different doses and schedules of ruxolitinib. Based on these, two phase III trials evaluated the efficacy and safety of ruxolitinib versus placebo in COMFORT I and versus BAT in COMFORT II in a population of patients with primary and secondary MF. In both phase III trials a starting dose of 20 mg orally BID was administered for patients with platelet counts from 200,000/ μ L and a lower starting dose of 15 mg orally BID in patients with baseline platelet counts from 100,000 to 200,000/ μ L.

Additional studies generated clinical data on the efficacy and tolerability of ruxolitinib in patients with MF and platelet counts from 50,000 to 100,000/ μ L. A starting dose of 5 mg BID with subsequent optional up titrations every 4 weeks by dose increments of 5 mg OD was evaluated in a phase II open label single arm study INC B18424-258 in a population of patients with platelet counts from 50,000 to 100,000/ μ L. Similarly, an expanded access program and phase IIIb study CINC424A2401 (JUMP) that recruited more than 2200 patients allowed the inclusion of patients with low platelet counts (50,000 to 100,000/ μ L) to be treated with a 5 mg BID starting dose.

Furthermore, a Phase Ib study (EXPAND) evaluating the safety and MTD of ruxolitinib in patients with lower baseline platelet counts (50,000– 100,000/ μ L) suggests that higher doses of ruxolitinib can be safely administered to patients with lower baseline platelet count. The maximum safe starting dose in this ongoing study was reported to be 15 mg BID for patients with platelet counts from 75,000 to 100,000/ μ L and 10 mg BID for patients with platelet counts from 50,000 to 75,000/ μ L.

Anemia may be ameliorated by lowering the dose of ruxolitinib or by concomitant use of erythropoietin stimulating agents and/or anabolic steroids (Reilly 2014). This approach may make particular sense in patients with anemia at the moment of treatment initiation with ruxolitinib in order to avoid further hemoglobin decrease, the need of blood transfusions or have them more frequently in patients already receiving regular transfusions for anemia.

An alternative strategy to start patients at 10 mg BID and titrate the dose up according to tolerability and response (Cervantes 2014, Harrison 2013) has anecdotally suggested improved tolerance and reduced adverse events yielding fewer treatment discontinuations and has been already included in treatment guidelines (Ho 2015, Reilly 2014).

[figure not shown]
Based on the above, a starting dose of 10 mg BID will be assigned to patients recruited in this phase II open label single arm study followed by gradual up titrations starting at week 12, based on efficacy and safety at the different evaluation visits. This approach assumes that starting at a lower dose may impact the rate of the initial hemoglobin decline and the nadir, by decreasing the level of JAK-mediated inhibition of hematopoiesis.

